intervention (contextualized CDS) on overuse and misuse of medical services. First, they are by definition standardized, meaning that physicians in both the control and intervention groups are seeing the “same” patient.³⁰ This experimental approach enables apples-to-apples comparisons (i.e. intrinsic risk adjustment) of clinical decision making, isolating the intervention as the sole changing variable. Second they assess actual performance in practice, rather than just skills.²² The third reason is that USP cases can be designed around ambulatory presentations for which there is evidence based consensus about what constitutes appropriate care.³¹ For instance, there is consensus that ordering radiographic studies on a patient presenting with uncomplicated lower back pain is an overuse of medical services. Similarly, ordering a malignancy work up on patient with weight loss in the setting of caloric deprivation is a misuse of medical services. The fourth reason is that USPs scripts can be customized around the particular CDS features we seek to assess. For instance, if we seek to assess whether alerts designed to inform clinicians when their patients are not adhering to medications in the setting of deteriorating chronic care management (e.g. a diabetic patients with elevated Accucheck readings in their log book) reduce unnecessary consultation of specialists, prescribing of additional medications etc...we will employ USP scripts that simulate such presentations.

For this project, 4 USP scripts with embedded contextual red flags and factors, drawn from our library of such cases will be selected. Their training and deployment will be managed by the UIC Graham Clinical Performance Center, which has extensive prior USP experience.^{7,32} The scripts will be modified and customized to assess the efficacy of the selected CDS innovations such that failure of CDS to prevent inattention to contextual red flags or factors in USP cases would result in a contextual error. Following the development of the 4 scripts, each script will be portrayed at 10 control visits without CDS support and 10 intervention visits with CDS support, divided across the two sites, for a total of 80 USP visits.

	Year 1	Year 2	Year 3	Year 4
Recruitment and Randomization of Real Patients				
Recruit 500 patients across two sites and assist with patient reported data entry (RA)				
Collect and 4C code audio recorded data (Project Manager and RA)				

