9.0 Data Analysis

Hypothesis 1: CDS tools that inform clinicians of contextual factors and prompt them to ask questions when there are contextual red flags should result in a reduction in contextual error.

From real patient encounters (i.e. observational assessment): Each visit is “Content Coded for Contextualization of Care” (“4C”).⁶ 4C coding consists of reviewing the medical record and listening to the audio to identify the presence or absence of each of the four steps to contextualize care: Are there contextual red flags? If so, did the clinician probe them? If so, did the patient reveal contextual factors? Note that patients sometimes reveal contextual factors without a probe.³³ Regardless, did the clinician incorporate the contextual factor(s) into the care plan? 4C enables care plans to be classified as either contextualized or inappropriate because of a contextual error. In the latter instance, 4C also pinpoints the cause of the error as either secondary to a failure to probe a contextual red flag or failure to incorporate a contextual factor into the care plan. Hence, 4C coding will ascertain whether contextualized CDS is associated with a reduction in contextual error. And, when contextual error rates are reduced it will ascertain whether the reduction is associated with a higher probing rate or a higher rate of addressing contextual factors revealed without a probe into the care plan.

From USP encounters (i.e. experimental assessment): Does not require 4C coding; instead we use checklists based on evidence based criteria for appropriate vs inappropriate care. We will recruit USPs to present with 4 different scripts, with counterbalancing of control vs. intervention EHR rules and specific USP scripts among physicians, so that each physician sees 2 intervention USPs with the contextualized CDS rules

active and 2 control USPs with no contextualized CDS. As in our past work, likelihood of probing contextual red flags and contextualizing care will be tested using mixed effects logistic regression models to control for case differences and clustering of cases within physicians.

Hypothesis 2: Contextualized CDS predicts improved health care outcomes defined as a resolution of the contextual error after the index visit.

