This analysis is based exclusively on data generated from the USP visits, in which physicians in the usual care and contextualized CDS groups see sets of "identical" patients for which misuse and overuse of medical services has been pre-defined. Utilizing our previously published methods,⁵ we will adopt the economic perspective of the patient and their third party payer, if any, with a time horizon of the expected consequences of care during the 30 days following the consultation. We consider only the direct consequences of care associated with diagnosis or misdiagnosis. We will not consider downstream costs beyond the initial recommendations from the consultation, and we will not consider societal costs not incurred by the patient or payer, such as lost productivity. We will include only resources related to the immediate diagnostic and therapeutic management at the index visit. Resources are direct medical costs in the case of unnecessary treatment and foregone direct medical costs in the case of under treatment.

Sample size calculations

Real patients (see Figure 5): Assuming, based on our prior research⁴ and data from the audit & feedback program,¹⁹ that contextual red flags with associated factors will be present in 50% of recorded visits, that 30% of patients approached will consent to participate, that physicians unaided will probe 50% of contextual red flags and that physicians unaided will contextualize care in 50% of visits with contextual factors, we propose to power the study for 80% power to detect an absolute increase in probe rate from 50% to 75% with contextualized CDS, and a corresponding increase in contextualization rates from 50% to 75%. Testing hypothesis 1 requires 58 patients with identified contextual factors per group, and therefore at least 145 patients consented and recorded per group. Testing hypothesis 2 requires at least 60 contextualized care plans in the intervention group and 60 non-contextualized care plans in the control group, which we expect to achieve with 80 identified contextual factors in the

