intervention group (requiring 192 recorded visits) and 120 identified contextual factors in the control group (requiring 288 recorded visits). Thus, to test all project hypotheses, we will approach and consent a sufficient number of patients (approximately 1600) to obtain recordings of 480 patients, randomize them to the intervention and control groups on a 2:3 basis (192 intervention, 288 control), and expect to identify contextual factors associated with red flags in 80 intervention and 120 control patients. As the primary care clinics at the participating sites see approximately 5,000 unique patients (UIC) and 25,000 (Loyola) annually, accrual is likely to require no more than 4-6 months.

Sample size (USPs): In our past work with USPs, physician made contextual errors approximately 80% of the time.⁷ Assuming that the contextualized CDS enhances physician attention to red flags and leads them to probe substantially more often (e.g. increasing probe rate from 50% to 75%) and attend to identified information (e.g. increasing plan rate from 50% to 75%), we would expect overall contextual errors to occur no more than 45% of the time, and 28 control and 28 intervention USP visits would provide 80% power to detect such a difference and test hypothesis 1.

In our past work, we found an overall median cost of error of \$194 when cases presented with contextual red flags, based on a median cost of \$231 when contextual errors occurred and a median cost of \$0 when contextual errors did not occur.⁵ Based on bootstrapped simulation from our cost data in that study, 40 control and 40 intervention USP visits provide 83% power to detect the expected cost reduction (a median of \$156) due to reduced contextual errors using a Wilcoxon rank-sum test with a significance level of $p<.05$. Accordingly, we will conduct 40 control and 40 intervention USP visits to provide sufficient power to test both study hypotheses. As the study comprises 4 USP visits (2 control, 2 intervention) per physician, we will recruit 20 physicians for this portion of the study.

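### Hypothesis 3 names no cost test, and the rank-sum test used for sizing ignores the physician and script balance that the hypothesis 1 model adjusts for

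*Combined protocol and SAP*

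**What the plan says.** The hypothesis 3 text in section 9.0 limits the analysis to USP visits. It opens the costing rules with "Utilizing our previously published methods" and then gives the economic perspective, the 30-day horizon and the resources to be counted. It gives no test, model or summary measure for comparing the arms. It describes visits "in which physicians in the usual care and contextualized CDS groups see sets of" matching patients, which reads as two sets of physicians.

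The sample-size text for USPs in the same section takes an overall median cost of $194 "when cases presented with contextual red flags, based on a median cost of" $231 with an error and $0 without. For the error rate under CDS it says "we would expect overall contextual errors to occur no more than 45% of the time", against about 80% in past work. It then gives 83% power with 40 visits per arm to detect a median reduction of $156 "due to reduced contextual errors using a Wilcoxon rank-sum test with a significance level of" p<.05. No other cost test appears in section 9.0.

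The design is crossed and balanced:

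- Physicians: "As the study comprises 4 USP visits (2 control, 2 intervention) per physician", with 20 physicians (section 9.0).
- Scripts: "each script will be portrayed at 10 control visits without CDS support and 10 intervention visits with CDS support" (section 6.0).

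For hypothesis 1 on these same USP visits, section 9.0 specifies "mixed effects logistic regression models to control for case differences and clustering of cases within physicians".

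**The concern.** A reader must either take the sizing test as the planned analysis or conclude that none has been set. If the rank-sum test is the analysis, it treats 80 visits as independent when they come from 20 physicians and four scripts. The plan thinks both factors worth adjusting for on one outcome and is silent on the other.

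Because each arm appears equally often within every physician and every script, differences between physicians and between scripts cancel from the arm comparison. They stay in the variance that the plain test uses, so the test is conservative and gives away precision that the counterbalancing has already bought. Cost is likely to be skewed with many zeros, so leaving the method open also leaves room to choose it after the data are seen. Section 10.0 gives the DSMB the task of approving the analysis plan, so the test should be in the text that it approves.

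**Working it through.** **The plan's own figure.** The 83% came from a bootstrap of an earlier study's cost data. The documents do not give those data, so the figure cannot be reproduced. As a proxy, take 40 vs 40 visits, a two-sided 5% tie-corrected rank-sum test, error rates of 80% and 45%, log-normal error costs with median $231, and $0 without an error. Simulated power is 80 to 81%. The stated 83% is plausible but unverified.

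**Why balance matters.** Write the variance of the cost ranks as between-script (S) + between-physician (P) + residual (R). In the balanced design, and with a constant CDS effect:

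- true variance of the arm difference in mean ranks ≈ R × (1/40 + 1/40)
- variance assumed by the plain test ≈ (S + P + R) × (1/40 + 1/40)

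The plain test is therefore at nominal size when S = P = 0 and below it otherwise. With physician and script both fixed, adjustment uses 19 + 3 = 22 degrees of freedom, leaving 80 − 1 − 1 − 22 = 56.

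**Calibration.** If $156 is the difference in arm medians, the intervention median is 194 − 156 = $38. With 45% errors, a further 5% of all visits must cost more than $38, which is 0.05/0.55 ≈ 9% of error-free visits. The simulation gives 11% of error-free visits a log-normal cost with median $60 (assumed) and error costs a log SD of 0.5 (assumed). With no script or physician differences this yields a median reduction of $158.

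**Simulation.** 20 physicians × 4 scripts, 2 + 2 visits per physician, 10 + 10 per script, two-sided 5%, 10,000 replicates (Monte Carlo standard error 0.2 points for size, 0.4 for power). Plain = tie-corrected rank-sum. Blocked = overall ranks regressed on arm, script and physician. All differences are assumed. SDs are on the logit scale of the error rate. The standard-error (SE) ratio is taken under the planned effect.

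| Assumed differences | Size %, plain / blocked | Power %, plain / blocked | SE ratio, blocked to plain |
|---|---|---|---|
| A. None | 5.0 / 5.1 | 79.0 / 78.9 | 1.00 |
| B. Script median costs $180–290 | 4.3 / 5.0 | 80.1 / 80.5 | 0.99 |
| C. As B, script SD 0.3, physician SD 0.5 | 4.4 / 5.2 | 80.1 / 81.6 | 0.97 |
| D. Script median costs $115–460 | 2.6 / 5.3 | 79.8 / 82.7 | 0.95 |
| E. As D, both SDs 0.5 | 2.3 / 4.9 | 79.0 / 84.0 | 0.92 |
| F. Script median costs $80–640, both SDs 1 | 1.2 / 5.0 | 79.4 / 88.7 | 0.85 |
| G. CDS effect varies by physician, SD 1, equal costs | 5.4 / 5.5 | 79.0 / 79.6 | 0.99 |
| H. CDS effect varies by physician, SD 1.5, equal costs | 5.6 / 6.0 | 77.1 / 78.4 | 0.98 |
| I. As C, plus CDS effect SD 1 | 4.4 / 5.4 | 79.3 / 81.1 | 0.96 |

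From A to E the gain runs from −0.1 (78.9 − 79.0) to 5.0 points (84.0 − 79.0).

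**Sensitivity.**

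- With every error-free visit at $0 (4,000 replicates), row A gives 80.4 / 80.1 and row E 81.7 / 86.0. With 30% of error-free visits carrying a cost, row A gives 78.4 / 78.2 and row E 77.6 / 82.5.
- A separate simulation with wider assumptions (script costs at 0.25 to 3 times, script SD up to 1, latent physician intraclass correlation up to 0.41) gives plain power of 67 to 85% and adjusted power of 81 to 94%. Its largest gain, 66.7 to 90.3%, needs very unequal script costs together with large script differences in error rate.

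**The case against.** The strongest reply is that no harm is shown. Counterbalancing already protects the arm comparison from confounding by script or physician. The plain test is at or below nominal size unless the CDS effect varies between physicians, and 40 visits per arm is not shown to be too few. This stands, and it makes the point one of efficiency and specification rather than validity.

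Second, a protocol often identifies its test through the sample-size text, and the rank-sum test is named there with its alpha. If that is the intention, the test is stated, but it is the one that drops the balance. If it is not, the analysis is unspecified. The text needs a change either way.

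Third, the cited costing paper may specify the comparison, and the sponsor's bootstrap may already carry script variation. Neither can be checked from the documents. The citation leads into the costing perspective, not into a test.

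Fourth, the gain depends on assumed variances, and no passage says which scenario is extreme. This also stands: the figures are illustrations.

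Finally, blocking has limits. When the CDS effect varies by physician its size is 5.5 to 6.0%, no better than the plain test, and a physician-level paired t test on script-centred ranks does not help in row H (size 5.6%, power 72.7%). A rank model also leaves the dollar difference as a descriptive result.

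**Conclusion.** The concern holds as a modest point for the sponsor to consider. The hypothesis 3 text names no comparison, and the only cost test in section 9.0 ignores balance that the plan uses for hypothesis 1 on the same visits. With no to moderate script or physician differences, adjusting gains about 0 to 5 points of power, and the standard error is 0 to 8% smaller. Larger gains need larger differences. The plain test's size falls from 5.0% to about 2.3% over that range, while the blocked test stays at 4.9 to 5.3%.

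These figures rest on assumed cost shapes and variances, a two-sided 5% level (the plan does not state sidedness), and a CDS effect that varies little between physicians. They neither confirm nor contradict the 83%, and they do not show that planned power is lost.

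**What to change.** In section 9.0:

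1. Name the hypothesis 3 analysis and let it account for script and physician. One option is to rank all 80 costs together and model the ranks on arm, script and physician, reporting the dollar difference descriptively. State whether the test is two-sided.
2. Say that the 83% refers to the unadjusted rank-sum test.
3. Align the wording that places physicians in two groups with the within-physician design, both here and in the USP rationale in section 6.0, which uses similar language.
4. Keep an arbitrary physician code on each USP visit. Section 8.0 rules out keeping names, not codes, and the hypothesis 1 model needs the code anyway.

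The cost is a few sentences, settled before the DSMB approves the plan. No visits or new data are needed. The statistical price is the 22 degrees of freedom if both factors are fixed, with a power loss of about 0.1 to 0.3 points when scripts and physicians do not differ.

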10.0 Data and Safety Monitoring

We believe this study is minimal risk. However, to ensure the safety of research participants and to comply with NIH policies, a DSMB will be formed in early months of the project and given responsibility to review and approve study methods and analysis plan for the research. The DSMB will be organized by [name] and will consist of senior, experienced clinicians and health services researchers. If deemed necessary by the IRB, the Principal Investigators will not be on the Data Safety and Monitoring Committee, thereby ensuring some level of independent review. When necessary, we will bring in experts from outside the project to serve on the committee. The DSMB will review interim data mid-way through the study using a predetermined stopping rule to determine whether the intervention group is being significantly benefitted (or harmed) over the control group and whether early stopping is necessary. In the rare event that an adverse event attributable to the CDS intervention is found, we will contact the patient's provider and document in the chart the potential error that was found.

One mid-trial (half of patients enrolled) comparison of rate of 4-6 month post-visit resolution of visit contextual red flag for intervention vs. control visits using a mixed effects logistic regression model with random effect of clinic/site and fixed effect of trial arm. An effect of trial arm that is significant at the $p<.01$ level in either direction will trigger early stopping of additional recruiting (however, in patients already recruited who have completed the study visit, we will continue to obtain and analyze their 4-6 month post-visit medical records)

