8.0 Data Collection and Management Procedures

- Patients: Data for this study will come from 3 patients sources: (a) Their medical record. These are contextual red flags (e.g. missed appointments, loss of control of a chronic condition); (b) a patient completed inventory that is tethered to their electronic medical record, eliciting both contextual red flags and contextual factors that are not likely to be present in the EHR. See appendix for items; (c) Audio recordings they collect of their encounter, from which contextual red flags and contextual factors will be noted, and whether the care plan is contextualized or contextual errors are present. The extraction of all these data follow the Content Coding for Contextualization of Care (“4C”) methodology as described in the proposal and previously published. These data will be accessible to the research assistant, project manager, and PI who are trained 4C coders, in a format that contains identifiers (MRNs). However, once they have extracted the data and paired data from the EHR with the audio coded data, identifiers are removed and replaced with arbitrary codes. They do retain, however, a crosswalk file between codes and MRNs separate from the research data so that they can follow up on patient chart based outcomes for the presenting red flag 4-6 months post index visit; once chart outcomes are extracted and tagged with the code, the crosswalk file will be destroyed. Beyond the coding team, data is only shared without identifiers. We will employ encryption on all audio recorders, and audio is immediately uploaded to a

secure research data approved server using a USB port following the visit. Access to the medical record is conducted by an RA trained in the “4C” method, as detailed in the proposal, which requires extracting specific information onto a spread – contextual red flags and factors as outlined in the research plan and detailed in our online and cited coding manual. In addition the patients note is linked to their data using a cross-walk file accessible only to the RA, project manager and PI, and then discarded after outcomes data is collected at 4-6 months, and identifiers are no longer needed.

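### The Principal Investigators, who are among the 4C coders, are kept off the DSMB only if the IRB asks, and nothing limits who sees interim results by arm

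*Combined protocol and SAP*

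**What the plan says.** Section 10.0 (Data and Safety Monitoring) sets up a DSMB that reviews and approves the study methods and analysis plan. On membership it says "If deemed necessary by the IRB, the Principal Investigators will not be on the Data Safety and Monitoring Committee", and adds that this has the effect of "thereby ensuring some level of independent review". Outside membership is also conditional: "When necessary, we will bring in experts from outside the project to serve on the committee".

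The same section gives the board its interim task: "The DSMB will review interim data mid-way through the study using a predetermined stopping rule". The look takes place when half the patients are enrolled and is a "comparison of rate of 4-6 month post-visit resolution of visit contextual red flag for intervention vs. control visits". An arm effect at p<.01 "in either direction will trigger early stopping of additional recruiting". Patients who have already had their study visit continue to have their 4-6 month records obtained and analysed.

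Section 8.0 (Data Collection and Management Procedures), on the patient records and audio held with identifiers, says: "These data will be accessible to the research assistant, project manager, and PI who are trained 4C coders". The same people keep the crosswalk file "so that they can follow up on patient chart based outcomes for the presenting red flag 4-6 months post index visit". Section 11.2 (Subject Confidentiality) repeats both statements.

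**The concern.** An interim comparison by arm is normally confined to people who have no further part in producing the data. Here the default runs the other way, since a PI may be a board member unless an outside body objects.

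Two things are at stake. The first is the standing of the board's decisions. A PI member would be approving a plan of the PI's own making and would share in deciding whether the trial stops for benefit or harm. The second is the flow of information. The interim endpoint is the Hypothesis 2 outcome, and the Hypothesis 1 outcome (contextual error) is coded by judgement from the audio and the chart. Someone who knows how the arms compare at the halfway point could then go back to coding the remaining visits or outcomes.

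**Working it through.** No figure in the plan is in dispute, so the check sets the sections side by side. The only arithmetic concerns timing.

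1. **Who may be on the board.** Section 10.0 excludes PIs on one condition, an IRB finding. No other section excludes them, and none excludes the project manager, the RA or other coders. The section describes the members as senior clinicians and health services researchers, a description that a PI could meet.

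2. **What the board sees.** Section 10.0 specifies a mixed effects logistic model with trial arm as the fixed effect, so the comparison is by arm. The section does not say whether the arms are labelled or masked for the board, who runs the model, or who else receives the result. No independent statistician is assigned.

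3. **What a PI also does.** Sections 8.0 and 11.2 name the PI as a trained 4C coder with access to identified data. Section 8.0 adds that the coders and the PI are the only people able to hear the audio. It assigns access to the medical record to an RA, so PI extraction of chart outcomes is possible but not stated. The coder role is explicit.

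4. **What blinding is stated.** Under Hypothesis 2, section 9.0 says that red flags are tracked by a blind method, that good and poor outcomes are defined in advance from the original red flag, and that outcomes are determined without knowledge of whether the visit was coded as contextualized. Blinding to arm is not named. For the 4C coding of visits under Hypothesis 1, no blinding to arm is stated.

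5. **What work is still open at the look.** Inputs: 480 recorded patients and accrual in no more than 4-6 months (section 9.0, sample size), and outcomes at 4-6 months (section 10.0). Assumption: even accrual.
   - Half enrolment: 480 / 2 = 240 patients, reached at 4/2 = 2 to 6/2 = 3 months.
   - Outcomes complete for that half: 2 + 4 = 6 months at the earliest, 3 + 6 = 9 months at the latest.
   - Accrual ends at 4 to 6 months. If the look waits for these outcomes, recruiting is expected to be over by then, and much of the audio coding could be done.
   - Outcomes for the other 240 patients fall due from 2 + 4 = 6 months to 6 + 6 = 12 months. Much of that extraction would still lie ahead.

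On the plan's own schedule, then, the work most clearly exposed is chart-outcome extraction for the second half of patients. Slower accrual, or a look taken before the first half's outcomes are complete, would leave more visits to code as well.

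**The case against.** The case on the other side has several parts, and much of it stands.

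- **The text permits PI membership but does not announce it.** True. The IRB may well have required exclusion, and the documents do not say. The weakness lies in the default.
- **The stopping rule is numeric and fixed in advance.** True, and this leaves little room for discretion over stopping. It does not restrict knowledge of the result, and section 10.0 still has the board determine whether stopping is necessary.
- **An aggregate result does not reveal any patient's arm.** True. A shift in coding between arms needs a coder who knows or can guess the arm. If coders are blind to arm, knowing the trend does them little good. If they are not, bias is possible even without an interim look. The documents do not settle which applies, because arm is not named in the blinding statements.
- **Outcome criteria are set in advance and tracking is blind.** This is a real safeguard and limits the concern for Hypothesis 2. It does not extend to visit coding.
- **The study is described as minimal risk.** That bears on participant safety, not on the integrity of the comparison.

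A reader might also infer that interim knowledge would reach the people who recruit. The documents do not support this. Sections 5.0 and 11.1 give patient calls and the consent contacts to the RA, nothing suggests that an RA would sit on the board, and on the planned schedule little recruiting would remain.

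**Conclusion.** The point holds as a weakness in a stated rule. The plan allows a PI who codes trial data to sit on the board that approves the analysis plan, sees the by-arm interim comparison and applies the stopping rule, and it places no limit on who else sees that comparison. Independence of the board is not assured.

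Two stronger readings go too far. One is that independence is already lost. That would require PIs to be members, which the text does not say. The other is that the false-positive rate rises by some stated amount. Any such figure would be fixed by an assumed coding shift between arms, would require coders to know each patient's arm, and would depend on how many visits or outcomes are still open. The documents supply no value for the shift and do not settle whether coders know the arm, so the size of any bias cannot be derived from them.

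The conclusion rests on the absence of any unconditional exclusion or access restriction elsewhere in the combined document. A DSMB charter or an IRB decision outside it could already close the gap. In that case the protocol need only be brought into line.

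**What to change.** In section 10.0, replace the conditional exclusion with an unconditional one. No PI, project manager, RA or other coder is a member of the DSMB or sees results by arm before final data lock. By-arm interim results go only to DSMB members and to a designated analyst who does not code visits or extract outcomes. PIs attend open sessions only.

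The cost is a few lines of text and the naming of that analyst. The board is already to be made up of senior clinicians and researchers, and the section already provides for outside experts. Sample size, visits, the intervention and the stopping threshold are unaffected. The change should be in place before the interim comparison is run.
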